difference in survival (3) patients primarily using heroin (n = 534): HR = .69, 13% difference in survival, and (4) the overall sample (n = 800): HR = .74, 10% difference in survival. We have chosen to use an alpha level that corrects for the number of primary hypotheses rather than the number of subgroup analyses as the latter approach would substantially increase the likelihood of making a type 2 error [24,25].

6. Explain procedures that will involve the subject

Process Evaluation

For our ongoing process evaluation we will conduct semi-structured interviews with key clinical team members, program directors, and patients at each of the health center sites. These interviews will take place at three time points – first in Year 1 prior to the randomized trial, once in Year 2, and again in Year 3 in order to obtain implementation feedback throughout the project. Participation in these semi-structured interviews will be voluntary, and all participants will complete informed consent as outlined in Item 9 below.

Providers. We will interview approximately 14 providers and program directors at each time point. Provider participants will not receive payment for their participation. Provider participants will be asked about their opinions on integrating substance use treatment into primary care, medication assisted treatment, contingency management, and barriers to implementation.

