Patients randomized to PATH will receive their OUD treatment in the FQHC on a flexible, individualized schedule. The PATH care team – a BHC, a Peer Recovery Specialist (PRS), a Psychiatric Nurse Practitioner, and an Addictions Psychiatrist – will provide patients with an evaluation/individualized treatment plan based on the standardized needs assessment from the ASAM Criteria interview and the SAMHSA Recovery Support Services Questionnaire. The treatment plan will focus on reduction of opioid use, psychiatric stabilization, pursuit of the patient’s individual recovery goals and meeting support service needs. The course of treatment is scheduled for 1 year, with medication induction occurring in Weeks 1-4, and then transitioning to maintenance in ensuing weeks. Behavioral Treatment is most intensive in Weeks 1-13 (twice weekly), dropping to weekly for Weeks 14-26, and then as needed in Weeks 27-52. Treatment components include:

1. Medication Assisted Treatment (MAT): The medical providers will offer MAT for addiction: primarily injectable extended-release naltrexone (XR-NTX) [26,27] and office-based buprenorphine (agonist treatment) [28]. Patients will initiate these treatments in our primary care settings, in some cases participating in an ambulatory detoxification / induction on site (**OP patients**), or being inducted after an inpatient detoxification (**IP patients**). Providers will also be trained and supervised to be able to diagnose, determine treatment recommendations, initiate, and maintain outpatient psychiatric treatment per the highest tier of these specifications of the ASAM Criteria. The personalized aspect of PATH emphasizes some patient choice, with the option to pivot from one medication to another based on patient response and preference. The flexible protocol will allow opioid dependent patients to: a) remain on or taper off a long-term agonist (buprenorphine); or b) convert to antagonist (XR-NTX).

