Primary Hypothesis 2: Clients in the PATH condition will demonstrate greater retention in treatment than clients in the SC condition. Retention is widely considered the leading proxy for clinical effectiveness in SUD treatment. A Cox proportional hazards survival analysis [5,6] will be used to determine whether the rate of dropout differs between the two treatment conditions. The analysis will account for right-censored data as some participants may not experience the event (i.e., treatment dropout, defined as absence from treatment for 30 days) during the period of observation. The analysis will include any necessary covariates. To establish the HTE for this outcome, the survival analysis will be repeated for each primary and exploratory subgroup identified above. Models will include a term for the subgroup variable and its interaction with treatment condition. Again, if the interaction term is significant, the treatment effect will be estimated separately at each level of the categorical variable that is used to define the subgroups. We anticipate that the proportional hazard assumption will be met as we expect the typical pattern of dropout in both groups (i.e., high hazard early, low hazard late). We will conduct standard residual-based analyses to evaluate proportionality and, in the event that the

proportional hazard assumption is violated, we will use extended Cox models that include a time-dependent covariate to model the non-proportionality [7]. The analyses will be performed using PROC PHREG.

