Power for the Primary Hypotheses. Power analyses were calculated for the primary hypotheses described above. The power analyses for Primary Hypothesis 1 were calculated following the recommendations of Liu and Wu [8]. The analysis was based on a corrected alpha of .025 (.05/2 primary outcomes), a compound symmetry covariance structure, an estimated abstinence rate of 25% in the SC condition (based on data from our prior study), a correlation between observations on the same patient of .50, and assuming 20% attrition at the final time point. For the smallest subgroup (patients primarily using prescription opioids: $n = 266$; 133 per condition), we will have 80% power to detect an approximately 15% difference in abstinence rates between the conditions (i.e., 25% in control vs. 40% in experimental; OR = 2.0). This projected difference is conservative and based only on the repeatedly demonstrated, similarly scaled differences contingency management yields when compared to standard treatment conditions [9-13]. The smallest detectable differences for the remaining subgroups and the overall sample are as follows using the same specifications: (1) patients recruited from IP setting ($n = 400$): 12%, OR = 1.8, (2) patients recruited from OP setting ($n = 400$): 12%, OR = 1.8, (3) patients primarily using heroin ($n = 534$): 9%, OR = 1.6, and (4) the overall sample ($n = 800$): 8%, OR = 1.5. The power analyses for Primary Hypothesis 2 were calculated following the recommendations of Lakatos [14]. The analysis was based on a corrected alpha of .025, no attrition as chart data will be available for all patients, and estimated dropout rate of 60% in the SC condition [15]. For the smallest subgroup (patients primarily using prescription opioids: $n = 266$; 133 per condition), we will have 80% power to detect a hazard ratio of .59 which corresponds to a difference in survival rates of approximately 18% between the two conditions. The smallest detectable hazard ratio for the remaining subgroups and overall sample are as follows using the same specifications: (1) patients recruited from IP setting ($n = 400$): HR = .65, 15% difference in survival (2) patients recruited from OP setting ($n = 400$): HR = .65, 15% difference in survival (3) patients primarily using heroin ($n = 534$): HR = .69, 13% difference in survival, and (4) the overall sample ($n = 800$): HR = .74, 10% difference in survival. We have chosen to use an alpha level that corrects for the number of primary hypotheses rather than the number of subgroup analyses as the latter approach would substantially increase the likelihood of making a type 2 error [4,16].

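### If the proportionality check fails, the SAP does not say which test decides Primary Hypothesis 2, so the .025 error rate is not controlled as written

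*SAP*

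**What the plan says.** In the SAP, under Primary Hypothesis 2, a Cox regression "will be used to determine whether the rate of dropout differs between the two treatment conditions". The event is a 30-day absence from treatment. The SAP then says "We anticipate that the proportional hazard assumption will be met", because both arms should show high early and low late dropout. Proportionality will be examined with residuals and, if it is violated, "we will use extended Cox models that include a time-dependent covariate to model the non-proportionality".

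Under Power for the Primary Hypotheses: "The analysis was based on a corrected alpha of .025, no attrition as chart data will be available for all patients". On multiplicity: "We have chosen to use an alpha level that corrects for the number of primary hypotheses rather than the number of subgroup analyses". Power is given for one hazard ratio per sample. For the prescription-opioid subgroup, "we will have 80% power to detect a hazard ratio of .59"; for the whole trial, Protocol item 5 gives "the overall sample (n = 800): HR = .74, 10% difference in survival". The sizing method cited is one for the log-rank statistic.

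Neither document states:
- what test or level counts as a violation;
- the form of the time-dependent covariate;
- which quantity then decides the hypothesis;
- whether the ordinary Cox result remains primary.

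On treatment intensity, Protocol item 6 (PATH) has behavioural treatment twice weekly to week 13, "dropping to weekly for Weeks 14-26, and then as needed in Weeks 27-52". Under Standard Care, intensive outpatient treatment usually lasts 3-4 months and is followed by outpatient care for up to 9 months.

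**The concern.** The model that tests a co-primary hypothesis is chosen from the trial's own residuals, and after a switch the hypothesis has no defined test. In an extended Cox model, log HR(t) = b1 + b2 g(t). The coefficient b1 is the log hazard ratio where g(t) = 0. That is day zero for g = t, and one time unit for g = log t, so recording time in months instead of days changes the coefficient and its p-value. Neither version tests retention over follow-up. The candidates for the deciding test (b1, b2, a joint 2-df test, the effect at a chosen month) can disagree, and the choice would be made with the data in view.

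The sponsor adopted .025 to correct for two primary hypotheses, and an open choice at this point can give part of that correction back. The stated power covers only a constant hazard ratio, so nothing supports the power of the fallback.

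The reason given for expecting proportionality is not sufficient. Two arms can both have high early and low late dropout while their hazard ratio changes over time.

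**Working it through.** **Inputs.** From the documents: alpha .025, 400 per arm, SC dropout 60% (retention S0 = .40), HR .74, 18-month trial. Not in the documents, so assumed: two-sided testing, level of the check (5%, also 10%), time function, retention horizon (12 or 18 months), hazard shape (Weibull .6 or exponential).

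**1. The plan's power figure.** Expected events = (n/2)[(1 - S0) + (1 - S0^HR)]. With .40^.74 = .5076, this is 400 x (.60 + .4924) = 437. Schoenfeld power = Phi(sqrt(437) x |ln .74| / 2 - 2.241) = Phi(3.147 - 2.241) = Phi(.906) = 81.7%. The retention difference is .5076 - .40 = 10.8 points.

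| n | HR | Power | Difference in retention |
|---|---|---|---|
| 800 | .74 | 81.7% | 10.8% |
| 534 | .69 | 81.4% | 13.1% |
| 400 | .65 | 81.0% | 15.1% |
| 266 | .59 | 79.6% | 18.2% |

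The stated 80% is reproduced with two-sided .025. One-sided .025 gives 87-88% and does not reproduce it.

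**2. Type I error of checking first and then choosing the model.** With no effect at any time, the overall Cox statistic Z1 and the check statistic Z2 are asymptotically independent. With the check at 5%, the trials that pass it contribute .95 x .025 = .02375. The trials that fail it add:
- *Time-centred treatment coefficient (uncorrelated with the check):* .05 x .025 = .00125, total .025.
- *2-df test* (reject if Z1² + Z2² > -2 ln .025 = 7.378): about .0138 by numerical integration, total .0375.
- *Uncentred treatment coefficient, correlation r with the check:* total .0265 (r = .3), .0294 (.5), .0342 (.7), .0378 (.8), .0427 (.9).
- *Either coefficient, each at .025:* P(|Z2| > 2.241) = .025, plus .025 x (.05 - .025) = .0006, total .049.

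With the check at 10% the totals are .025, .038, .027-.045 and .049.

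**3. Simulation with no effect** (800 patients, 60% dropout, 10,000 trials per column, Monte Carlo SE about .0016, check at 5%).

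| Rule | Weibull .6, 18 months | Exponential, 12 months |
|---|---|---|
| Cox always | .0222 | .0260 |
| Switch, centred t | .0223 | .0260 |
| Switch, uncentred t | .0343 | .0401 |
| Switch, uncentred log t | .0265 | .0379 |
| Switch, 2-df (t; log t) | .0369; .0361 | .0384; .0408 |
| Switch, either coefficient (t; log t) | .0538; .0489 | .0540; .0538 |

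Smaller simulations over 18 months with Weibull shapes .6 and 1.0 gave 2.6-4.2% for the uncentred coefficient and 3.0-4.1% for the 2-df test.

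**4. Power.** At a constant HR of .74 the check fails in about 5% of trials. In those trials the uncentred coefficient has 49-62% power, against about 82% overall for Cox. The overall loss is then .05 x (82 - 62) = 1.0 to .05 x (82 - 49) = 1.7 points; simulations put it at about 1 to 3.

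With a late benefit (HR .95, then .6), power fell from 76-97% with Cox throughout to 40-65% with the switch on the uncentred coefficient. The month of the change is a further assumption; a change at month 3 gives figures close to these. The loss belongs to that term. A 2-df test in the same setting did at least as well as Cox.

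**5. The schedules side by side.** The first PATH reduction follows week 13 (91 days, 3 months); the SC step-down comes at 3-4 months. These nearly coincide. PATH changes again after week 26, with no matching SC step. SC then runs to about 12-13 months (3-4 plus up to 9) and PATH is scheduled for one year.

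**The case against.** A reader might infer that the switch necessarily raises the error above .025. The documents do not support that. They fix neither the time function nor the deciding term, and with centred time the error stays at .025. The lowest uncentred figure (.0265) is within one Monte Carlo standard error of .025. The residual checks may also be graphical, with no formal level. This objection stands, and it limits the claim to error that is not controlled.

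The most striking figures are conditional. Given a failed check, the uncentred coefficient is falsely significant in 9-33% of trials with no effect, and has 49-62% power at HR .74. If hazards are truly proportional, that situation arises in about one trial in twenty. This stands too, so only the overall figures should carry weight.

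A reader might also infer from the step-downs that non-proportional hazards are likely. The first reductions nearly coincide and total durations are similar; only the week-26 change clearly differs. Non-proportionality is possible but has not been shown to be likely.

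Finally, the fallback is written in advance, and the SAP's Sensitivity analyses section promises comparisons under different distributional assumptions. Both help transparency. Neither names the test that decides the hypothesis, and no other section does.

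**Conclusion.** The point holds as a gap in the specification of a confirmatory test. The SAP has a stated, data-dependent rule and no defined deciding quantity after it operates. With a 5% check, type I error runs from .025 to about .05 according to a choice the plan leaves open. In the scenarios simulated, most natural choices give .026 to .043, an excess of up to about 2 points over .025.

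Under proportional hazards the cost in power is small. The more serious case is a benefit that appears late, where an uncentred treatment coefficient can miss a retention gain that the ordinary Cox test would usually detect. That case rests on an illustrative effect pattern, and neither document predicts it. All figures depend on the assumed check level, time function, horizon and hazard shape. The correction should be made before the data are seen; it does not call the design or sample size into question.

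**What to change.** State in the SAP that Primary Hypothesis 2 is decided by one test, the log-rank test or the Cox treatment coefficient (choose one), at two-sided .025, whatever the proportionality check shows. This matches the power calculation. It keeps the error at .025 (simulated .022 and .026) and leaves power at 81.7% for HR .74, with 437 expected events against 420 needed by the Schoenfeld formula. Report the proportionality check, the extended Cox model (with its time function and reference time stated) and retention at fixed months as supportive description of how the effect changes over time.

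The cost is SAP wording only, with no extra patients or data. The downside is that, under non-proportional hazards, the single hazard ratio is an average and must be read with the retention curves. The fixed test can also lose some power against a 2-df test, or against a test aimed at an early effect. If the sponsor prefers one of those, it can be named instead, provided it is fixed in advance and does not depend on the check.

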Primary Hypothesis 1: Clients in the PATH condition will demonstrate higher rates of confirmed substance abstinence (hair and UA verified) during treatment and at follow-up than clients in the SC condition. Confirmed abstinence is the “gold standard” of direct clinical outcomes in SUD research. A mixed effects logistic regression model [2,3] will be used to compare the binary outcome of hair and urinalysis-confirmed abstinence in the two treatment conditions at months 3, 6, 9, 12, 15, and 18. Mixed effects models have advantages of traditional repeated measures approaches in that they allow for missing observations, accommodate measurements made at different time points, provide flexibility in modeling the variance-covariance matrix, and permit the estimation of both group and random patient-specific effects. The model will include terms for treatment condition, time, and their interaction, and the binary baseline abstinence variable along with any other necessary covariates. We will follow the recommendations of Varadhan and Seeger [4] to test heterogeneity of treatment effect (HTE). We have identified two primary subgroup analyses to be performed: (1) setting [IP (n = 400) vs. OP (n = 400)] and (2) type of opioid [heroin (n = 534) vs. prescription (n = 266)]. We will use similar mixed effects logistic regression models (described above) that will additionally include terms for the specific subgroup variable and its interaction with treatment condition. In the event that the interaction is significant, the treatment effect will be estimated separately at each level of the categorical variable that is used to define the subgroups. In addition, we will conduct an *exploratory* subgroup analysis for medication type (agonist vs. antagonist/drug free). We anticipate simple time trends (e.g., linear or quadratic) for the mixed effects models; however, we will use linear spline models in the event complex time trends are observed, such as non-linear trends that cannot be approximated by simple polynomials in time [2]. These analyses will be performed using PROC GLIMMIX.

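### The fixed .025 per primary hypothesis is valid, but Holm's step-down never rejects less at the same familywise .05 and costs almost nothing to adopt

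*SAP*

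**What the plan says.** The SAP paragraph on power for the primary hypotheses, repeated in Protocol item 5, sets the level for Primary Hypothesis 1 (abstinence): "The analysis was based on a corrected alpha of .025 (.05/2 primary outcomes". For Primary Hypothesis 2 (retention) it says: "The analysis was based on a corrected alpha of .025, no attrition as chart data will be available for all patients". It explains the choice thus: "We have chosen to use an alpha level that corrects for the number of primary hypotheses rather than the number of subgroup analyses".

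The SAP sections that describe the two primary analyses give no significance level and no decision rule, so the power paragraph is the only statement of how the two tests are controlled. Neither document mentions a step-down, a hierarchy, or passing alpha from one hypothesis to the other after a rejection. Neither says whether tests are one- or two-sided, though the hypotheses are worded directionally, for example: "Clients in the PATH condition will demonstrate higher rates of confirmed substance abstinence (hair and UA verified".

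**The concern.** Read as a decision rule, the split tests each hypothesis at .025 whatever the other shows. Once one primary has been rejected at .025, familywise control at .05 no longer requires the other to be held at .025. Holm uses this. It orders the two p-values, tests the smaller at .025 and, if that is rejected, tests the larger at .05. It controls familywise error at .05 under any dependence between the tests. It can never reject less than the fixed split.

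What is at stake is power, not validity. A trial in which one primary is clear and the other has a p-value between .025 and .05 would claim one result under the split and two under Holm.

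**Working it through.** **Inputs from the SAP.**
- Alpha .025 for each primary.
- Abstinence: "an estimated abstinence rate of 25% in the SC condition (based on data from our prior study"; within-patient correlation .50, with 20% of patients lost by the last visit; six visits ("in the two treatment conditions at months 3, 6, 9, 12, 15, and 18"). For the smallest subgroup, 133 per arm: "we will have 80% power to detect an approximately 15% difference in abstinence rates between the conditions", that is 25% against 40%.
- Retention: 60% dropout in SC; detectable HR .59 at n = 266 and .74 at n = 800.
- Detectable abstinence difference in the full sample: 8 points at n = 800.

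**Assumptions not in the documents.** Two-sided tests, and a correlation r between the two test statistics, shown over a range.

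**Step 1. Reproduce the stated 80%.** The critical value at two-sided .025 is 2.241, at .05 it is 1.960, and z for 80% power is 0.842.

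Abstinence, time-averaged difference, n per arm = (2.241 + 0.842)² × [p₁q₁ + p₂q₂] × [(1 + 5 × .5)/6] / d²:
- Smallest subgroup: 9.505 × (.1875 + .2400) × .5833 / .15² = 105.3. Dividing by .80 for attrition gives 131.7, so 132 against the stated 133. Power at 133 is 80.4%. A one-sided .025 test would give about 87%, so two-sided is the reading that fits.
- Full sample, 8 points, 400 per arm: 75.5% if 20% are missing at every visit, and 80.7% if average loss is 10% (building to 20% at the last visit).

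Retention, events = (N/2) × [.60 + (1 − .40^HR)] and power = Φ(√(events/4) × |ln HR| − 2.241):
- HR .59, N = 266: 135 events, 79.6%.
- HR .74, N = 800: 437 events, 81.7%.

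So 80% at two-sided .025 is a fair description of both hypotheses at their smallest detectable effects.

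**Step 2. Full cost of the split.** An effect with 80% power at .025 has mean statistic 3.083. At .05 its power is Φ(3.083 − 1.960) = 86.9%. The split costs 6.9 points.

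**Step 3. What Holm recovers, both hypotheses at 80%.** Power for one hypothesis is P(p₁ ≤ .025) + P(.025 < p₁ ≤ .05 and p₂ ≤ .025). With independent tests this is .80 + .0693 × .80 = .855. Power to win both is .64 + 2 × .0693 × .80 = .751. Bivariate normal integration gives the other rows.

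| r | Each, split | Each, Holm | Both, split | Both, Holm |
|---|---|---|---|---|
| 0 | 80.0% | 85.5% | 64.0% | 75.1% |
| .3 | 80.0% | 85.0% | 66.6% | 76.6% |
| .5 | 80.0% | 84.6% | 68.7% | 77.8% |
| .7 | 80.0% | 84.1% | 71.3% | 79.4% |
| .9 | 80.0% | 83.2% | 75.0% | 81.5% |

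With the reproduced full-sample powers in place of 80% (abstinence 80.7%, retention 81.7%), Holm gives 86.2% and 87.0% at r = 0, and 85.3% and 86.0% at r = .5.

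**Step 4. Away from that point.**
- Other hypothesis at 50% power: the one at 80% gains 3.5 points (r = 0) or 2.0 (r = .5). The weaker one gains about 9 (50% to 58.9–59.0%).
- Other hypothesis null: at most 0.2 points (.0693 × .025 = .0017 at r = 0).
- Abstinence difference of 15 points with 400 per arm: power at .025 is already 99.9%, and Holm adds less than 0.1 point. Retention is then almost always tested at .05. It gains 6.9 points if it has 80% power at .025, or 6.5 (81.7% to 88.2%) at the reproduced power for HR .74. At HR .59 with n = 800 it too is at 99.9% and gains nothing material.
- Chance of rejecting at least one primary: identical under both rules (96.0% at r = 0).

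**Step 5. Error rates.** Under the global null, the familywise error is the same for both rules (.049 at r = 0). With one hypothesis null and the other at 80% power, the null one is falsely rejected with probability .80 × .05 + .20 × .025 = .045 at r = 0, and .042 at r = .5, against .025 under the split. The ceiling is .05.

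**The case against.** The strongest reply is that nothing is broken. The split is stated in advance and controls familywise error, and the trial reaches its 80% target after paying for it. All of that stands.

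The size is also conditional. A reader might infer that the plan gives up about 5 points of power on each hypothesis outright. The documents do not support that. The figure holds when both effects are real and each sits at its smallest detectable value. The plan's own abstinence projection is larger: it calls 15 points conservative, and at that difference in the full sample abstinence has nothing left to gain.

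A reader might also take the SAP's remark about type II error as conceding that the split between primaries is too costly. It is not. The remark concerns correcting for the number of subgroup analyses.

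Two costs are real. Every rejection that Holm adds has a p-value between .025 and .05, so its 97.5% interval includes the null. And when only one effect is real, the false-positive rate of the other hypothesis rises from 2.5% to about 4.2–4.5%.

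Finally, Holm needs one p-value per hypothesis. The abstinence model has condition, time and their interaction without naming the contrast that decides, and the retention model may move to a time-dependent effect. That gap is real, but the fixed split needs the same two p-values. Planning at .025 is also compatible with testing by Holm, so the power figures need not change.

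**Conclusion.** The point holds as an optional efficiency improvement. The plan's one stated rule is uniformly dominated by Holm at the same familywise .05. The benefit is about 4.6–5.5 points per hypothesis, and 9–11 points for winning both, when both effects are real with 80% power at .025 and r lies between .5 and 0. It is close to zero for a hypothesis whose partner is null, or whose own power is already near 100%. It does nothing for the chance of winning at least one primary.

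These sizes rest on two-sided testing, supported only by its reproducing the stated 80%, and on a correlation that the documents do not give. It would go too far to call the split an error or the trial underpowered because of it: the split is valid, and the stated power for both primaries reproduces at .025.

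**What to change.** Add to the SAP, before unblinded results are seen, a statement that the two full-sample primary hypotheses are tested by Holm at two-sided familywise .05 and that decisions rest on the Holm-adjusted p-values. Keep the existing detectable differences at .025 as conservative planning figures. If 97.5% intervals are reported, say that they are conservative and can include the null for a hypothesis rejected at the second step.

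The cost is a sentence or two of text, with no new patients, data or models. The downsides to accept openly are intervals that do not always match the decisions, and a false-positive rate of up to .05 for a null primary when the other effect is real. The single contrast that supplies each p-value should be named at the same time, as either rule requires it.
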